7.2.2 Sampling technique

Eligible patients will be approached during their phase 2 CR consultation with the CR multidisciplinary team. Convenience sampling will be used to ensure sufficient recruitment to the study.

7.3 Recruitment

7.3.1 Sample identification

Participants will be identified by a member of the university research team who will regularly attend CR initial assessment clinics. This member is also employed at Bedford Hospital as a Cardiac Rehabilitation Exercise Specialist. They will have access to the clinic list and medical notes prior to the consultation, where they can be screened to check who may be eligible for the study. This is usual practice as part of the role of a Cardiac Rehabilitation Exercise Specialist. All members of the research team involved in recruitment will have an NIHR research passport and will have completed secondary GCP (Cardiac Rehabilitation Exercise Specialist). Eligible patients will be approached by the Cardiac Rehabilitation Exercise Specialist to ask if they would be interested in volunteering to take part in the study.

Participants will be approached after their initial CR appointment by a member of the research team to invite them to take part in the study. An introduction to the study will be given and the patient will be given a participant information sheet (PIS) to take away. A consent to contact form will be completed that allows the research team to call the patient to discuss the study further and explore whether they are interested in participating. It is optional and refusal to do so does not in any way affect their usual standard of care. If they complete a consent to contact form, the patient will be given at least 24 hours to read the PIS and discuss with friends and family, to carefully consider their participation in the study.

7.3.2 Consent

Only patients with capacity to consent will be considered eligible for the study. If the patient would then like to participate in the study, an informed consent form will be given for them to complete and sign. Should a patient lose capacity during the follow up period, they will be withdrawn from the study. Identifiable data or blood samples already collected with consent would be retained and potentially used in the study. No further data or samples would be collected or any other research procedures carried out.

For an individual to have capacity to consent they will: understand the purpose and nature of the research; understand what the research involves, its benefits (or lack of benefits), risks and burdens; understand the alternatives to taking part; be able to retain the information long enough to make an effective decision; be able to make a free choice; be capable of making this particular decision at the time it needs to be made (though their capacity may fluctuate, and they may be capable of making some decisions but not others depending on their complexity).

8 ETHICAL AND REGULATORY CONSIDERATIONS

8.1 Assessment and management of risk

Physical Activity

As patients will be asked to do light intensity physical activity, there is a very small risk of injury and falls. However, risks will be kept very minimal by asking the patient to complete a health questionnaire to check for any contraindications. If any symptoms become evident during the study, participants will be asked to stop straight away and monitored for an appropriate amount of time. There will also always be a first aider available on site.

Blood Collection

There is a small risk of bruising associated with blood collection. To reduce this, research members will be trained in the appropriate blood collection technique, which adhere to published guidelines.

There is a very small risk of contamination from blood sample collection. However, these risks will be minimized by using protective equipment, disinfecting all re-useable equipment and screening all participants with a health questionnaire before they take part in the study. Individuals will be asked not to take part in the study if they have a blood borne disease or virus.

Further heart abnormality findings

An ECG will be carried out by a suitably trained professional prior to each condition taking place. If any changes to the electrical activity of the heart are observed, the study will not be carried out and the participant will be advised to get in contact with their GP or an ambulance will be called, depending on what the findings are.

Echocardiogram scanning

There is a small risk of a skin reaction to the gel used during scan. However, it is a hypo-allergenic gel. To minimise this risk further, a small patch test will be carried out prior to the study taking place. If there is any redness around the area applied, the scan will not go ahead. Further to this, there may be slight discomfort to the participant when the scan is taking place, through either a cold gel, slight pressing on the chest or being unclothed on their top half. It will be highlighted to them that it is important to inform the researcher of any discomfort and that they are free to stop the study at any time. If any areas of concern are highlighted during the echocardiogram, the participant's GP will be informed by writing a letter to them.

If an adverse event occurs, there is a qualified advanced first aider (also trained in AED and gas) on site in the laboratory at all times. There is access to first aid equipment (first aid box, AED, oxygen) and a telephone, where an ambulance would be called. The GP will be notified of any event that occurs during data collection. Likewise, if there are any incidental findings regarding the results obtained during the study, the GP will be notified via a letter detailing the findings.

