In addition to poor cardiometabolic health following an MI, an individual can develop structural problems within the myocardium due to myocardial damage and necrosis (Thygesen, et al., 2007). If not managed appropriately, this causes left ventricular (LV) hypertrophy and reduced LV ejection fraction, thus resulting in LV remodeling (Azvedo, et al., 2016). This leads to poor prognostic outcomes for the individual, ultimately resulting in chronic heart failure. This can include shortness of breath, decline in functional capacity and difficulty with active daily living tasks, as well as mental health problems and poor health related quality of life (Lesman-Leegte, et al., 2009). Therefore, interventions need to be identified to prevent these myocardial changes following an MI.

Data from the Bogalusa Heart study suggests that individuals with metabolic syndrome had significantly higher values for LV mass, end-diastolic posterior wall thickness, septal wall thickness and LV end diastolic diameter (Patel et al., 2009). Further to this, high blood pressure, high fasting glucose, high triglycerides and low HDL-C are independently associated with eccentric hypertrophy of the LV. As breaking up sitting time can acutely improve cardiometabolic risk markers, it is plausible that there could be benefits to cardiac function as

well. This would be of great importance to cardiac patients who are at high risk of suffering a secondary event and thus requires evaluation.

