Participants will be asked to refrain from any alcohol and caffeine for 24 hours prior to each visit, as well as avoid exercise for 72 hours and complete an overnight fast. This will be explained to them during the preliminary visit. To monitor this, they will be asked prior to participation per visit whether they have fasted/ when they last ate and drank.

Participants will be asked to perform an overnight fast for at least 10 hours before arrival and minimise active travel to the laboratory (e.g. use a car for travel). They will rest for 30 minutes to achieve a steady state before baseline blood pressure (two measures with 2 minutes rest between each and the average taken) and blood samples are taken. Baseline cardiac function measures (global strain, ejection fraction and systolic volume) will be measured using an echocardiogram scan, as well as an electrocardiogram (ECG) to ensure there are no electrical contraindications to the heart which would make the participant unsuitable to complete the study intervention including ST depression / elevation or any arrhythmias. Baseline mood and wellbeing measures will then be assessed using questionnaires.

Following baseline measures, a standardised breakfast will be consumed (see meals section below) and participants will then commence the experimental condition. See Figure 1 for schematic of experimental conditions.

The three experimental conditions for this study are:

- 1) Uninterrupted sitting for 6 hours.
- 2) Sitting interrupted with 5 minutes of static standing every 30 minutes.
- 3) Sitting interrupted with 5 minutes of light intensity stepping every 30 minutes using a metronome at the intensity determined during preliminary testing. This replicates active recovery time currently performed in a phase III CR class.

A lunch meal will be provided at 12:00 during each condition. During sitting periods, participants will be able to read books, magazines or newspapers and/or watch TV, DVDs or media streaming services. Participants will be transported to the toilets and food consumption areas using a wheelchair to ensure activity is minimised and standardised between conditions.

Standardised food and water intake

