Each meal will provide approximately 30% of estimated daily energy requirements. This will be calculated for each individual participant using a prediction equation based on individual's height, weight and gender. Breakfast will consist of bran flakes, whole milk, and a honey and granola bar and will consist of 54% carbohydrate, 34% fat and 12% protein. Lunch will consist of a chicken sandwich, salted crisps and jammie dodger biscuit (54% carbohydrate, 34% fat and 12% protein). The macronutrient composition of the meals are in general agreement with guidelines recommended for a balanced diet (Public Health England, 2016). Participants will be encouraged to consume their meal within 15 minutes. The time taken will be recorded in the first condition and this time will then be replicated in the latter two conditions. Water will be available for the participants ad libitum during their first experimental condition visit. This volume of intake will be recorded and the same amount provided in the following two conditions spread over the day.

Data collection

Finger prick capillary whole blood samples will be collected at baseline, 30, 60, 120, 180, 210, 240, 300 and 360 minutes throughout the conditions to allow later analysis of glucose, triglycerides, HDL-C, and insulin. Blood samples will be taken after the hand is pre-warmed in warm water for approximately 5 minutes. Blood pressure and heart rate will be measured 5 minutes before each of the blood samples are taken. Cardiac function measures and mood and wellbeing will be measured at baseline and post-condition

[figure not shown]

Figure 1: Schematic of experimental protocol, PA, physical activity; ECG, electrocardiogram.

Biochemical analyses

600 μ l of whole capillary blood will be collected using EDTA microvette tubes that will be centrifuged (Heraeus Pico 17 microcentrifuge; Thermo Scientific, Loughborough, UK) at 2000 \times g for 5 min. The plasma will then be pipetted into 0.5 mL eppendorf tubes and stored at -80° for later analysis. Plasma glucose and triglyceride concentrations will be analysed via enzymatic colorimetric methods using a benchtop analyser (Pentra 400; HORIBA ABX Diagnostics, Montpellier, France). Plasma insulin concentrations will be determined using an enzyme linked immunosorbent assay technique (Mercodia, Uppsala Sweden).

Blood pressure and heart rate

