Blood pressure and heart rate will be measured in an upright, seated position using an automated device (Omron M5-1 automated oscillatory device, Omron Matsusaka Co. Ltd., Matsusaka, Japan). The same arm will be used for BP measurement each time throughout the study, which will be taken on the left arm unless there is preference for the right arm due to any potential previous medical conditions. A single measure will be taken at each time point apart from baseline where two measures will be taken with a 2 minute rest between each.

Cardiac function

In a laboratory, the patient will be asked to undress from the waist up and lay on the medical couch in the left lateral decubitus position. Here, a scanning gel will be applied to the echocardiogram probe. This forms part of the echocardiogram system; Vivid 7, GE Medical, Mius Ltd., Gloucester, UK). Parasternal and apical views will be acquired (Armstrong and Ryan., 2012). Once these images are collected and stored, the gel will be removed from the probe and chest. All images will be stored anonymously, where participants will be given a participant ID number. All image analysis will be completed using Echopac software (GE Healthcare, Version 113, GE healthcare, Chicago, Illinois, United States).

LV mass, LV mass index (adjusted for height), LV end diastolic volume, LV end systolic volume, wall motion score index (WMSI), E/A ratio, relative wall thickness, and deceleration time will be measured. These measures will be used to calculate left ventricular function.

Mood and wellbeing

The Positive and Negative Affect Scale (PANAS) questionnaire (Watson et al., 1988) will be used to assess current mood and subjective wellbeing measured using the National Wellbeing Measurement. These questionnaires will be completed at baseline and immediately after

cardiac function measures post-condition. There is a significant correlation post cardiac event and poor mental health (Chadda, et al., 2016). This questionnaire will therefore measure whether breaking up sitting time regularly within this population will improve mental health measures. PANAS is a valid questionnaire, which can be modified to measure changes in mood across a day, without losing its validity (Watson, et al., 1988). If incidental findings of anxiety or depression occur, the GP shall be informed via a letter sent directly to them.

Data analyses

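### Minor safety gap: a concern recognised during the echocardiogram leads only to a GP letter, which cannot affect the session about to start, whereas an ECG change in the same baseline block stops it

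*Protocol*

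**What the plan says.** In the Protocol, section 5 (Experimental Protocol), the echocardiogram and the ECG are both baseline procedures at each condition visit. The ECG is given a suitability purpose: "to ensure there are no electrical contraindications to the heart which would make the participant unsuitable to complete the study intervention". What comes next is also fixed: "Following baseline measures, a standardised breakfast will be consumed (see meals section below) and participants will then commence the experimental condition".

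Section 8.1 then sets out the responses.

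- **ECG:** "If any changes to the electrical activity of the heart are observed, the study will not be carried out". The participant is directed to the GP or an ambulance is called, according to the finding.
- **Echocardiogram:** "If any areas of concern are highlighted during the echocardiogram, the participant's GP will be informed by writing a letter to them".
- **Incidental findings in general:** "if there are any incidental findings regarding the results obtained during the study, the GP will be notified via a letter detailing the findings".

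The scan is repeated at the end of each visit: "Cardiac function measures and mood and wellbeing will be measured at baseline and post-condition" (section 5, Data collection).

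**The concern.** Section 8.1 expects that some concerns will be noticed while the scan is in progress, with the participant present. The only consequence it attaches is a letter. A letter has no effect on a session that starts the same morning, and it may not be answered before the next visit, which can follow after 72 hours.

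The protocol already accepts that a cardiac finding at baseline can make someone unsuitable for the day's condition, but it limits that check to electrical findings. Its own Background says that after an infarction "an individual can develop structural problems within the myocardium due to myocardial damage and necrosis", and a scan can show such problems when the ECG does not. At stake is the safety of a participant within three months of an infarction who has an urgent structural finding, no ECG change and no symptoms.

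**Working it through.** No figure in the plan depends on this point, so the check is a comparison of the text.

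**1. Same block, different consequences (sections 5 and 8.1).**

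| | ECG change | Echocardiogram concern |
|---|---|---|
| When | Baseline, before each condition | Baseline, and again after the condition |
| Session withheld? | Yes | Not stated |
| Graded by urgency? | Yes: GP or ambulance | No |
| Stated action | Stop and refer | Letter to the GP |

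**2. Does another section supply the missing hold?**

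- Section 7.1.2 excludes unstable coronary disease but has no echocardiographic criterion. It and the low-risk requirement in section 7.1.1 govern entry; they are not responses to something new seen at a visit.
- The symptom stop in section 8.1 needs symptoms.
- The first aider, AED, oxygen and ambulance call in section 8.1 are tied to an adverse event.
- The general rule for incidental findings is again a letter.

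None of these acts on a symptom-free imaging finding with an unchanged ECG.

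**3. Which findings could be known in time?** The scan will yield structural and functional measures: "LV end systolic volume, wall motion score index (WMSI), E/A ratio, relative wall thickness, and deceleration time will be measured" (section 5, Cardiac function). Images are stored and analysed in separate software, with no timing given, so these derived measures cannot be assumed to be available before the session. Section 8.1 does refer to concerns raised during the scan itself. The point is therefore confined to what is recognised live.

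**4. Exposure after a baseline concern that is not acted on.** This describes exposure, not harm.

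- Session length: 6 h × 60 = 360 min.
- One 5-minute bout in each 30-minute cycle: 360 / 30 = 12 bouts; 12 × 5 = 60 min.
- 30 minutes of sitting and then 5 minutes active: 360 / 35 = 10.3, so 10 full bouts; 10 × 5 = 50 min.

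The standing or stepping condition would thus involve about 50 to 60 minutes of activity; the range arises because the schematic is not shown. The sitting condition involves none.

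**5. Room for lost sessions (section 7.2.1).** 18 / (1 − 0.20) = 22.5, rounded up to 23. The difference of 23 − 18 = 5 is the 20% dropout allowance, already committed.

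**The case against.** The strongest reply is that the protocol is silent rather than wrong. The letter hands an imaging finding to the GP and was not written as a rule about the session. The two tests also have different roles: the ECG screens for suitability, while the echocardiogram supplies outcomes. Abnormal scans are expected after an infarction, so stopping for every one would be unworkable.

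The exposure is also mild. Stepping is held at RPE 8-11, is matched to a rehabilitation warm-up, and is likened to the active recovery of a phase III class. Patients are recruited through the rehabilitation clinic after their notes have been screened.

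Much of this stands. It keeps the point minor and confines it to findings that may need prompt attention, beyond stable changes from the index infarction. It does not remove the point. Section 8.1 is where the protocol sets its safety responses. Beside an ECG rule that both stops the session and grades the response, a letter-only rule for the scan can be read as deliberate.

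Three stronger readings are tempting, and the documents do not support them:

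- A reader might infer that staff are told to proceed after a worrying scan. The general sequence leads from baseline to the condition, but nothing says that the session must go ahead after such a finding.
- A reader might infer that ventricular volumes or wall motion scores will be in hand and ignored before the session. The timing of image analysis is not given.
- A reader might infer a count of participants at risk, a bias in the results or a contradiction in eligibility. No rate of concerning scans is given, and nothing in the text supports the other two.

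**Conclusion.** The point holds as a minor patient-safety improvement. For a concern recognised during the echocardiogram, the only stated consequence cannot affect the session that follows the baseline scan, while the neighbouring ECG rule can. The same lack of an urgent route applies at the post-condition scan, when the participant is still on site.

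Its size cannot be estimated beyond the exposure shown above. The remaining risk is small: participants are low risk, activity is very light to light, and the ECG check, the symptom stop and the emergency equipment all still apply. The conclusion assumes only that some urgent structural findings can be recognised live without an ECG change or symptoms; it assumes nothing about how often.

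**What to change.** Keep the GP letter and add to section 8.1, under Echocardiogram scanning, wording to this effect:

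> *Where any echocardiogram shows, while it is being performed, a finding that may need prompt medical attention (beyond stable changes expected after the index MI), staff will direct the participant to the GP or call an ambulance according to its urgency, as for the ECG. If the finding is made at baseline, that day's session is withheld. No further session takes place until the GP or the treating cardiac team confirms that the participant may continue.*

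Confirmation is needed because a GP reply alone is not clearance. The rule covers the post-condition scan too, including the one after the last condition.

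**Cost.** The change uses a scan already taken, an escalation route already written and GP contact already planned. The person scanning must judge urgency, and section 8.1 specifies suitable training for the ECG only, so the protocol should say who makes that judgement. Deferral fits the washout, which has a 72-hour minimum and no stated maximum. A few sessions may be deferred or lost. Since 23 already includes the dropout allowance, losses beyond it would rely on the replacement provision in section 7.2.1, which is pragmatic and depends on the study timeline. Under section 8.2, REC review is needed first if the sponsor judges the amendment substantial.

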8.2 Research Ethics Committee (REC) and other Regulatory review & reports

Before the start of the study, a favourable opinion will be sought from the NHS REC.

- Substantial amendments that require review by NHS REC will not be implemented until that review is in place and other mechanisms are in place to implement at site.
- All correspondence with the REC will be retained.
- It is the Chief Investigator's responsibility to produce the annual reports as required. The Chief Investigator will notify the REC of the end of the study.
- An annual progress report (APR) will be submitted to the REC within 30 days of the anniversary date on which the favourable opinion was given, and annually until the study is declared ended.
- If the study is ended prematurely, the Chief Investigator will notify the REC, including the reasons for the premature termination.
- Within one year after the end of the study, the Chief Investigator will submit a final report with the results, including any publications/abstracts, to the REC.

Regulatory Review & Compliance

Before patients are enrolled into the study, the Chief Investigator will ensure that appropriate approvals from participating organisations are in place. Specific arrangements on how to gain approval from participating organisations are in place and comply with the relevant guidance. For any amendment to the study, the Chief Investigator, in agreement with the sponsor will submit information to the appropriate body in order for them to issue approval for the amendment. The Chief Investigator or designee will work with sites (R&D departments at NHS sites as well as the study delivery team) so they can put the necessary arrangements in place to implement the amendment to confirm their support for the study as amended.

Amendments

If the sponsor wishes to make a substantial amendment to the REC application or the supporting documents, the sponsor will submit a valid notice of amendment to the REC for consideration. The REC will provide a response regarding the amendment within 35 days of receipt of the notice. It is the sponsor's responsibility to decide whether an amendment is substantial or non-substantial for the purposes of submission to the REC.

Amendments will also be notified to the *national coordinating function of the UK* country where the lead NHS R&D office is based and communicated to the participating organisations (R&D office and local research team) departments of participating sites to assess whether the amendment affects the NHS permission for that site.

In all instances the protocol will describe:

- The process for making amendments.
- Who will be responsible for the decision to amend the protocol and for deciding whether an amendment is substantial or non-substantial?
- How substantive changes will be communicated to relevant stakeholders (e.g., REC, R&D, regulatory agencies).
- How the amendment history will be tracked to identify the most recent protocol version.

